**NCT# 04552132**

**May 2, 2022**

## Pain Assessment Protocol

This study protocol was approved by the Institutional Review Board of Saint Louis University, Saint Louis, MO (Protocol Number 31359). Patients were recruited for this study from the patients seen at the Center for Advanced Dental Education at Saint Louis University from September 2020 through March 2022. Informed consent was obtained from each patient for participation in this study. The following inclusion criteria were utilized for participation in the study: adults fully able to provide informed consent, with restorable, symptomatic molar teeth (reporting  $\geq 20$ mm on the VAS during the previous 24 hours) seeking endodontic therapy. Patients where both Ibuprofen and Acetaminophen were contraindicated, patients with chronic pain issues for which they regularly need to consume analgesics, and patients having taken analgesics or antibiotics within the previous 6 hours were excluded from this study.

The first patient treated in the study was randomized by coin toss, followed by an alternating pattern thereafter for the 2 groups: GentleWave (GWS) (n=16) or EndoActivator (EA) (n=17). Prior to their clinical evaluation, the patients marked on: 1) a 100mm VAS instrument where they felt best represented their degree of pain experienced at that moment, and 2) a 2nd 100mm VAS instrument their maximum level of pain during the previous 24 hours. Clinical evaluation of the patient included percussion and palpation testing, periodontal probing measurements, thermal pulp sensibility testing using a cold source (Endo Ice), and an evaluation of tooth mobility. Radiographic examination (XDR Radiology, Los Angeles, CA) included bitewing, straight-on periapical, angled periapical, and 4X4 cm high-resolution limited field of view cone beam computed tomography (CBCT) (CAREstream 9600-CAREstream Dental, Atlanta, GA) imaging.

Following the administration of topical anesthetic (20% Benzocaine), the same high-level of anesthetic was administered to all patients, in order to standardize the number of injections received by the participants. If supplemental anesthesia was required, intrapulpal injections were performed for vital teeth and periodontal ligament injections were performed for necrotic teeth.

Rubber dam isolation and the surgical operating microscope were used throughout the treatment procedure. All deficient existing restorations and caries were removed. If inadequate isolation existed to perform the root canal treatment within an isolated environment, SoundSeal (Sonendo Inc., Laguna Hills, CA), a light-cured composite resin, was used to facilitate proper isolation.

Canal patency was achieved, and working length (WL) was determined using a #10 C-file and Root ZX II electronic apex locator (EAL) (J. Morita USA, Irvine, CA). WL was defined as being 1mm short of full tone on the EAL for patients in the GWS group (per the recommended Sonendo protocol) and 0.5mm short of full tone on the EAL for the EA group. All canals were instrumented to a size #20/.06 Vortex Blue nickel titanium rotary file (DENTSPLY Tulsa Dental Specialties, Tulsa, OK). 5.25% sodium hypochlorite (NaOCl) was administered using a 30-gauge, side-vented needle (ProRinse Probes-DENTSPLY Tulsa Dental Specialties, Tulsa, OK) with each successive file placed into the canal.

For the GWS group, 70% isopropyl alcohol placed on a dry cotton pellet was used to clean and dry the tooth. After having created a suitable platform using SoundSeal, the choice of

GWS cycle was determined according to the clinical situation and the corresponding manufacturer-recommended protocol  (Fig 1).

**Fig 1.** GentleWave System Cycles

Case Type	3% NaOCl	Distilled Water	8% EDTA	Distilled Water
Necrotic	4 Minutes	30 Seconds	1.5 Minutes	15 Seconds
Vital	5 Minutes	30 Seconds	2 Minutes	15 Seconds
Extended	5 Minutes	30 Seconds	2 Minutes	15 Seconds
Low	0.5% NaOCl	Distilled Water	8% EDTA	Distilled Water
	8 Minutes	30 Seconds	2 Minutes	15 Seconds

Settings were chosen based off of the proximity of root apices to vital structures such as the inferior alveolar nerve or maxillary sinus: 'Extended'>2mm, 'Necrotic' or 'Vital' 1-2mm, 'Low'<1mm

After completion of the preprogrammed GWS cycle, the canals were flushed with saline. For obturation, gutta-percha cones were selected that would extend 0.5mm beyond the end point of mechanical instrumentation, in order to facilitate obturation 0.5mm short of full tone on the EAL. The canals were dried using sterile paper points. Hi Flo BC Sealer (Brasseler USA, Savannah, Georgia) was expressed directly into the canal. Cones were placed, and seared off at the opening of each canal orifice using a heated System B unit (SybronEndo, Glendora, CA). The chamber was cleaned of excess sealer using a cotton pellet moistened with water, then rinsed and air dried with an air/water syringe. A sterile sponge was placed on the chamber floor, and the access opening was temporized with Cavit (3M ESPE, Neuss, Germany). Straight-on and angled periapical radiographs were exposed postoperatively.

For the EA group, instrumentation was performed as described above, but to 0.5mm short of full tone on the EAL, and the canals and chambers were flooded with 5.25% NaOCl. The

small EA tip (ISO 15/.02) was placed 2mm short of WL and activated vertically, in 2-3mm strokes for 30 seconds within each canal, as per the manufacturer's directions . The canals were subsequently flushed with fresh 5.25% NaOCl and then the irrigant was reactivated with the EndoActivator for an additional 30 seconds within each canal. Fresh sodium hypochlorite was again applied, and then removed by retracting the plunger on the syringe. A total of five milliliters of 5.25% NaOCl was used to irrigate each tooth during each procedure for patients within the EA Group. All canals were then irrigated with 3 milliliters of 17% EDTA using a 30-gauge, side-vented needle for a total of 1 minute. Canals and chamber were once again evacuated by retracting the plunger on the syringe and then a final flush with 3mL of saline was delivered using a 30-gauge side-vented needle. Canals were then dried with sterile paper points. The same single-cone obturation technique was used as for the GWS group.

Prior to leaving the clinic, the patient was provided an 8.5X11 inch, pre-stamped envelope containing 4 blank VAS forms to be filled out by the patient at 24 hours, 48 hours, 72 hours, and 96 hours postoperatively, as well as 4-days' worth of Ibuprofen (600mg Ibuprofen X 16 tablets) (Ascend Laboratories, LLC, Parsippany, NJ) and Acetaminophen (650mg Acetaminophen X 16 tablets) (Perrigo, Allegan, MI). The printed patient instructions were to take 1 tablet of Ibuprofen every 6 hours as needed for pain. If the Ibuprofen did not provide adequate pain relief, then the patient was instructed to also take 1 tablet of Acetaminophen every 6 hours as needed for pain. If the patient maximized the Ibuprofen and Acetaminophen intake and still required additional pain relief, then patient was instructed to call the clinic and a prescription would be provided for Tramadol 50mg X 12 tabs, to be taken every 6 hours as needed for pain. The patients were provided with a Pain Pill Log to record what analgesics were

taken at what times. After ninety-six hours postoperatively, patients were instructed to mail, or physically return, back to the clinic the large envelope with the 4 completed VAS forms, the Pain Pill Log, as well as any unused analgesics. Patients who properly returned all of the requested paperwork were compensated with a \$75 Visa gift card.

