#### Pain Assessment Statistical Analysis

Data was compiled and analyzed by a biostatistician at two different time periods. Therefore, participants that were seen between 09/2020-06/2021 were analyzed separately from those seen between 07/2021-03/2022. Data points for pain assessment and analgesic intake were plotted for visualization. A Shapiro-Wilk test of normality indicated a non-normal distribution of the pain data. Due to the skewness observed, a non-parametric analysis was utilized.

The level of pain recorded from each postoperative VAS was compared to the patient's preoperative VAS score to determine if their pain level had increased or decreased. A two-sided Fischer's Exact Test for Count Data was then used to determine whether postoperative pain decreased relative to preoperative pain scores more often in one group as compared to the other group.

Results were considered significant if the  $p \leq 0.05$ .

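### Allocation by alternation after a single coin toss, with no concealment described, leaves the unadjusted between-arm comparisons open to selection bias of unknown size

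*Combined protocol and SAP*

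**What the plan says.** Under Pain Assessment Protocol, allocation is described in one sentence: "The first patient treated in the study was randomized by coin toss, followed by an alternating pattern thereafter for the 2 groups". The resulting arms are 16 (GWS) and 17 (EA). Nothing in the document describes concealment, an independent allocator or blinding. It does not say who recruited, or whether the arm was known before consent and the eligibility decision.

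Entry was open to "adults fully able to provide informed consent, with restorable, symptomatic molar teeth" with a VAS of at least 20 mm in the previous 24 hours. Two preoperative scores were taken: current pain, and "their maximum level of pain during the previous 24 hours". Treatment visibly differs by arm. For example, "WL was defined as being 1mm short of full tone on the EAL for patients in the GWS group", while the EA group used a different length and a different device.

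Under Pain Assessment Statistical Analysis, a two-sided Fisher test asks whether "postoperative pain decreased relative to preoperative pain scores more often in one group as compared to the other group", and "participants that were seen between 09/2020-06/2021 were analyzed separately from those seen between 07/2021-03/2022". The section does not say which preoperative score is the comparator. Under CBCT Healing Assessment and statistical analysis, Pearson chi-squared tests compare the 3Droot and Ctooth outcomes in 12 GWS and 14 EA patients. None of the three tests has a covariate, and no baseline comparison between arms is described.

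**The concern.** Only the first assignment is random; each later one follows from the one before. Whoever treated a patient knew the arm, so the next arm was knowable in the clinic. Judging a tooth restorable involves discretion. The sequence is tied to the order in which patients were treated, so recruitment or scheduling could in principle steer a patient to one arm. The documents do not say whether the people who treated also recruited.

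The tests therefore rest on assumed comparability of the arms, and the analysis neither checks it nor adjusts for it. Comparing each patient with their own preoperative VAS does not supply it. If postoperative pain rises less than one-for-one with preoperative pain, the arm that starts worse will tend to show more decreases without any treatment effect. At 12 months, an imbalance in pulp status or preoperative lesion size would pass straight into the healing comparisons.

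**Working it through.** **Allocation (figures from the protocol).** 16 + 17 = 33. Strict alternation of 33 patients gives 17 to the arm that starts and 16 to the other, so the stated split is what results if the toss gave EA. Predictable assignments: 33 − 1 = 32, and 32/33 = 97.0%. If 16 and 17 are only the patients analysed, the count is N − 1 of a larger N. Recalled at 12 months: 12 + 14 = 26, so 33 − 26 = 7 were not.

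**Chance imbalance, for scale.** The documents give no SD, so 25 mm and 15 mm are assumed. The standard error of the baseline gap is SD × √(1/16 + 1/17) = SD × 0.3483.
- SD 25 mm: 8.71 mm. A gap of at least 10 mm arises by chance with probability 0.25, and of at least 20 mm with probability 0.02.
- SD 15 mm: 5.22 mm. 10/5.22 = 1.91, probability about 0.06; 20/5.22 = 3.83, probability about 0.0001.

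A 20 mm gap would therefore mean strong selection, extreme at SD 15 mm.

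**Effect of a gap on the Fisher test (all inputs assumed).** No treatment effect; preoperative mean 55 mm with the gap split equally around it; postoperative mean 30 or 45 mm; pre-post correlation 0.2 or 0.5; VAS held within 0-100.

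*Scenario (a): the gap carries into the postoperative mean as correlation × gap.* One setting can be checked by hand, ignoring the 0-100 limits: SD 25, correlation 0.2, postoperative mean 45, gap 10.
- SD of the change = 25 × √(2 × 0.8) = 31.6 mm.
- Higher arm: mean decrease 60 − 46 = 14; Φ(14/31.6) = 67.1% decreased.
- Lower arm: mean decrease 50 − 44 = 6; Φ(6/31.6) = 57.5% decreased.
- Spurious difference: 9.6 percentage points.

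Over the four settings at SD 25 mm, simulation gives spurious differences of 5-10 points at a 10 mm gap and 11-19 at 20 mm. Fisher false-positive rates are:

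| Scenario (a) | 10 mm gap | 20 mm gap |
|---|---|---|
| Pooled 16 v 17, SD 25 mm | about 3-6% | 6-14% |
| Pooled 16 v 17, SD 15 mm | 0.2-9% | 1-33% |
| One period, assumed 8 v 8 or 8 v 9, SD 25 mm | 0.3-4.3% | 0.8-8.5% |
| Pooled, SD 25 mm, comparator is the 24-hour maximum with its 20 mm floor | 2.5-4.3% | 2.9-8.0% |

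With no gap, the pooled rate at SD 25 mm is 2.9-3.2%, because Fisher's test is conservative at this size. The very low rates at SD 15 mm arise where nearly everyone improves: with postoperative mean 30 and correlation 0.5, Φ(25/15) is about 95%. Rank ANCOVA on preoperative VAS stays near 5%, as this set-up ensures.

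*Scenario (b): equal postoperative means despite the gap, so selection does not act wholly through measured VAS.* At SD 25 mm, pooled Fisher rejects in 5.5-9.3% (10 mm) and 15.8-31.4% (20 mm). Rank ANCOVA rejects in 5.6-8.7% and 6.5-18.8%.

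Nothing comparable can be calculated for 3Droot or Ctooth, because the documents give no basis for linking baseline status to healing.

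**The case against.** - **The scheme is disclosed and cannot be changed.** The alternation is stated openly, recruitment ended in March 2022 and the document is dated May 2022. This stands; it limits the remedy to reporting and analysis.
- **The plan does not claim randomised effects.** A reader might infer that it presents its results as such. It does not: only the first patient is said to be randomised, and the analysis sections speak of differences between groups. Relabelling alone would therefore add little; the baseline table and adjusted analysis do the useful work.
- **Bias is not shown.** A reader might go from 97% predictability to biased results. The documents do not support that step: predictability gives an opportunity only to someone who knew the previous assignment, and the 16/17 split fits the rule having been followed, though it cannot exclude selection.
- **The illustration is mild for the analysis actually planned.** Within one period at SD 25 mm, scenario (a) stays below 5% at a 10 mm gap. This stands for that scenario. In scenario (b) the per-period rates reach 6.0% at 10 mm and 17.1% at 20 mm.
- **The simulated rates depend on the SD.** They do, which is why two are shown. They are not evidence of size in either direction.
- **Adjustment is not a cure.** Correct, as scenario (b) shows. Rank ANCOVA also pools the two periods and changes the outcome scale, so it belongs as a sensitivity analysis and not as a replacement.

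**Conclusion.** The concern holds as a risk of bias and should be fixed. Every assignment after the first was predictable from the one before (32 of 33 if 16 and 17 are all allocated), no concealment is described, and none of the three named tests accounts for a baseline difference between arms. Whether selection happened, in which direction and how strongly cannot be derived from the documents. On assumed inputs, the effect on the pooled Fisher test ranges from negligible to a false-positive rate of about one in three. The top of that range needs a 20 mm gap at SD 15 mm, far beyond chance. For the two 12-month tests the risk is qualitative only. Confidence is high about the allocation method; nothing here establishes harm to the results.

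**What to change.** 1. Tabulate by arm both preoperative VAS scores, pulp status (vital or necrotic) and preoperative lesion volume, for all allocated patients and again for the 26 recalled.
2. Add a sensitivity analysis at 24, 48, 72 and 96 hours: rank-based ANCOVA of postoperative VAS on arm, preoperative VAS and recruitment period. Name which preoperative score is the comparator in the Fisher analysis, use that one, and repeat with the other. Include every patient with a returned form at that time and state the number analysed by arm.
3. When reporting, describe allocation as quasi-random (alternation after one coin toss) and the between-arm results as open to selection bias.

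Cost: one table, four small models (eight fits with both scores) and some wording, with no new patients or visits. Lesion volume may need measuring on existing preoperative scans for up to 7 patients. The price is a weaker causal claim and imprecise models on at most 33 patients, and selection on unmeasured factors remains.

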#### Pain Assessment Statistical Analysis

Data was compiled and analyzed by a biostatistician at two different time periods. Therefore, participants that were seen between 09/2020-06/2021 were analyzed separately from those seen between 07/2021-03/2022. Data points for pain assessment and analgesic intake were plotted for visualization. A Shapiro-Wilk test of normality indicated a non-normal distribution of the pain data. Due to the skewness observed, a non-parametric analysis was utilized.

The level of pain recorded from each postoperative VAS was compared to the patient's preoperative VAS score to determine if their pain level had increased or decreased. A two-sided Fischer's Exact Test for Count Data was then used to determine whether postoperative pain decreased relative to preoperative pain scores more often in one group as compared to the other group.

Results were considered significant if the  $p \leq 0.05$ .

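### Pain data are split into two calendar periods for an administrative reason, and no combined GWS v EA pain comparison of the 33 patients is described; if none was done, power was lost

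*Combined protocol and SAP*

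**What the plan says.** All references are to the combined protocol and SAP.

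- Pain Assessment Statistical Analysis, first paragraph: "Data was compiled and analyzed by a biostatistician at two different time periods". The next sentence opens with a word of consequence and states that "participants that were seen between 09/2020-06/2021 were analyzed separately from those seen between 07/2021-03/2022". No other reason for the separation is given.
- Same section, next paragraph: each postoperative VAS is classed as decreased or not against the preoperative score. A two-sided Fisher exact test asks whether decrease occurred "more often in one group as compared to the other group". This sentence names no period. Significance is p ≤ 0.05.
- Pain Assessment Protocol: patients came from "Saint Louis University from September 2020 through March 2022", which is exactly the two analysis periods joined. The first patient "was randomized by coin toss, followed by an alternating pattern thereafter for the 2 groups", giving 16 GWS and 17 EA. No change in criteria, treatment or allocation at July 2021 is reported.
- Pain Assessment Protocol, postoperative instructions: patients took home "4 blank VAS forms to be filled out by the patient at 24 hours, 48 hours, 72 hours, and 96 hours postoperatively", so the comparison arises at four time points. The text says that "Patients who properly returned all of the requested paperwork were compensated", but not how many patients returned forms.
- CBCT Healing Assessment: 12 GWS and 14 EA patients were recalled at 12 months. The document is dated May 2, 2022.

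**The concern.** The date on which an analyst receives data does not define a patient population. Nothing in the design makes patients seen before and after July 2021 different studies. If the separation governs the Fisher test, which is the natural reading, the trial's 33 patients are never compared as randomised groups in one pain test.

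Two things are then at stake. First, each test rests on fewer patients and has less power than one test of everyone. Second, the two periods can give different answers, and the text has no rule for which counts. It also does not give the number of patients per arm in each period, so a reader cannot weigh the two results.

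**Working it through.** The plan states no power, effect size or expected rates, so there is no figure of its own to reproduce.

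**Inputs from the document:** 16 GWS and 17 EA; alternating allocation; periods of 10 and 9 months; two-sided Fisher test at p ≤ 0.05. **Assumptions:** period sizes, the proportion decreased in each arm, and full return of forms.

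**Step 1: plausible period sizes.**
- *Uneven split.* A patient recalled at 12 months by May 2, 2022 was treated by about May 2, 2021, inside the first period. If the recall was complete by that date, the first period holds at least 12 GWS and 14 EA. Strict alternation keeps the arms within one of each other, so 14 EA implies at least 13 GWS. The first period is then at least 13 + 14 = 27, and the second at most 33 − 27 = 6 (3 v 3). So 27/6 is the most even split on this reading.
- *Near-even split.* If the recall section was written later, it says nothing about period size. Steady recruitment would put 33 × 10/19 = 17.4 patients in the first period, roughly 8 v 8 and 8 v 9.

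**Step 2: what a test needs, with no rates assumed.** Suppose every GWS patient improves.
- All patients: 16/16 v 12/17 is just significant. p = [C(17,5) + C(16,5)]/C(33,5) = (6188 + 4368)/237336 = 0.044. Required gap: 5/17 = 29 points.
- 13 v 14: 13/13 v 9/14 is just significant. p = [C(14,5) + C(13,5)]/C(27,5) = (2002 + 1287)/80730 = 0.041. Required gap: 5/14 = 36 points.
- 3 v 3: the most extreme table, 3/3 v 0/3, gives p = 2/C(6,3) = 2/20 = 0.10. This period cannot be significant.
- 8 v 8: 8/8 v 3/8 is needed. p = 2 × C(8,5)/C(16,5) = 112/4368 = 0.026. Required gap: 5/8 = 62.5 points.

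**Step 3: power at one time point, unadjusted.** Power = Σx Σy Bin(x; n1, p1) × Bin(y; n2, p2) × 1[Fisher p(x, y) ≤ 0.05], summed over all tables. Where two values are shown they are GWS better / EA better; a single value holds for both.

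| Decreased, better v worse arm | All 33 (16 v 17) | 27/6: first period (13 v 14) | 27/6: second period (3 v 3) | Near-even: 8 v 8 | Near-even: 8 v 9 |
|---|---|---|---|---|---|
| 95% v 50% | 82/86% | 73/79% | 0% | 28% | 40/51% |
| 90% v 50% | 65/69% | 56/62% | 0% | 22% | 32/39% |
| 95% v 60% | 62/69% | 50/59% | 0% | 13% | 20/31% |

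From unrounded values, the first-period loss at 27/6 runs from 86.1 − 78.5 = 7.6 to 62.2 − 49.5 = 12.7 points. In the near-even case the loss per period runs from 69.3 − 39.5 = 29.8 to 86.1 − 28.3 = 57.8 points.

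**Step 4: conflicting results.** With the near-even split, exactly one period is significant with probability a(1 − b) + b(1 − a). At 95% v 50%, GWS better: 0.283 × 0.596 + 0.404 × 0.717 = 0.46. Over both directions the ranges are 46–50%, 40–44% and 28–36% for the three scenarios. An example where both miss: 8/8 v 4/8 (p = 0.077) and 8/8 v 5/9 (p = 0.082); together 16/16 v 9/17 gives p = 0.003.

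**Step 5: cost of stratifying.** Exact Cochran-Mantel-Haenszel power with 8 v 8 and 8 v 9 strata is 82.7/86.4%, 65.4/69.8% and 62.5/69.5%, against pooled Fisher 82.4/86.1%, 64.7/69.3% and 62.2/69.3%. A 25/8 split gives nearly the same values. Stratifying costs nothing.

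**Step 6: smaller effects.** Pooled power is 20/26% at 90% v 70% and 12/20% at 95% v 80%. Neither analysis is informative there.

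**The case against.** The strongest reply has four parts.

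*A combined test may exist.* The separation sentence precedes the text on plotting and normality. The Fisher test comes in a later paragraph that speaks only of two groups. A reader might infer that no combined test was run; the document does not establish that. This stands, and it makes the harm conditional. It does not remove the reporting gap, because no later sentence rejoins the periods.

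*The loss may be modest.* A reader might assume two halves of equal size and conclude that most of the power was lost. The document does not support this as the main case. Its only clue to period size, the 12-month recall read with the document date, points to 27/6 or beyond, where the first period keeps most of the power. That clue is itself an inference, since the recall section could have been added after the date on the document. Both cases should therefore be shown.

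*The scenarios are favourable.* They assume differences of 35 to 45 points. Patients entered with symptoms and were given analgesics, so high rates of decrease in both arms are plausible, and pooling would then rescue little. This stands.

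*Multiplicity can absorb the gain.* At Holm's strictest step over four time points (0.0125), pooled power is 60/67%, 42/47% and 33/41%. That is below the unadjusted first-period power at 27/6, and close to the chance that at least one unadjusted near-even period is significant (57/65%, 46/53%, 31/40%). This also stands: against unadjusted period tests, the gain would be one error-controlled answer, not more detections.

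A further tempting argument is that the healing analyses compare the arms without a period split, so the trial pooled elsewhere. That does not follow. The recalled patients may all come from the first period, leaving nothing to split.

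**Conclusion.** The point holds in a conditional form. It is firm that the only stated reason for the split is administrative, that no combined or period-stratified pain comparison is described, and that there is no rule for reading two period results. Whether power was actually lost depends on whether the Fisher tests were run per period.

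If they were, the size depends on an unstated split and unstated rates. The loss is about 8 to 13 points for the first period at 27/6, with a second period that cannot be significant. It is about 30 to 58 points per period if the split was near-even. These figures assume full form return and large differences; for small differences both analyses are weak.

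A reader might also infer a biased treatment effect. The split does not cause one: alternation keeps the arms within one patient of each other in each period, so the period comparisons are like with like. The consequence is lost precision and an unclear reading.

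**What to change.** State whether a combined pain comparison was done, and report it if so.

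If it was not:
- At each of the four time points, make the main comparison GWS v EA in all patients who returned forms, on the stated decreased/not-decreased outcome.
- Use an exact Cochran-Mantel-Haenszel test stratified by period (or pooled Fisher), with an estimate and 95% confidence interval.
- Give the number of patients per arm in each period, and show period-specific results as descriptive only.
- Label the analysis post hoc if it is new.

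The cost is a re-run on data already held and some revised wording; no patients are added. The downsides are the post hoc label, an effect averaged over periods (hence the descriptive period results), and little or no gain in detections over the unadjusted period tests if the four time points are also adjusted for multiplicity. That adjustment, and which preoperative VAS serves as baseline, are separate questions that this change does not settle.

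### The unit and time point of the Fisher test on the four postoperative pain scores are not defined, and neither natural reading reliably holds a 5% error rate for the pain conclusion

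*Combined protocol and SAP*

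**What the plan says.** The Pain Assessment Protocol allocates patients to "GentleWave (GWS) (n=16) or EndoActivator (EA) (n=17") and gives each of them "4 blank VAS forms to be filled out by the patient at 24 hours, 48 hours, 72 hours, and 96 hours postoperatively".

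Under Pain Assessment Statistical Analysis, "The level of pain recorded from each postoperative VAS was compared to the patient's preoperative VAS score", so that each form is classed as an increase or a decrease. The next sentence applies one two-sided Fisher test, in the singular, to the question "whether postoperative pain decreased relative to preoperative pain scores more often in one group as compared to the other group". The section sets significance at p ≤ 0.05. It also states that "participants that were seen between 09/2020-06/2021 were analyzed separately from those seen between 07/2021-03/2022".

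The section does not name a primary day, the unit counted in the table, a rule that reduces four results to one per patient, a repeated-measures method, or an adjustment for multiple tests.

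**The concern.** Fisher's exact test needs independent counts. A patient's four increase/decrease indicators come from the same tooth and are set against the same baseline, so they will tend to agree. The text describes a test in the singular, fed by every form, and names no day. It therefore leaves two analyses open.

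- **Pooled.** The table counts scores, up to 4 × 16 = 64 against 4 × 17 = 68. The effective sample is smaller than it appears, and the p-value is too small.
- **Per day.** Each table counts patients, one score each, and each test is sound. There are then four tests at 0.05, and any one of them could be reported as the pain result.

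Both readings are multiplied by two if the recruitment periods are tested separately. What is at stake is whether p ≤ 0.05 can be taken at face value for the claim that one irrigation system reduces postoperative pain more often than the other.

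**Working it through.** The plan gives no power or error-rate figure to reproduce beyond the nominal 0.05.

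**Inputs from the document:** 16 v 17 patients, four scores each, two-sided Fisher test, p ≤ 0.05, two periods analysed separately.

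**Assumptions, not in the document:** the same decrease rate in both groups (null hypothesis), 50–90%; within-patient correlation of the indicator (ICC) 0.3–0.7; period sizes of about 8 v 8 and 8 v 9.

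**1. Pooled, both periods combined (64 v 68 scores).** Beta-binomial counts out of 4 per patient, 20,000 simulated trials per cell, percentage rejected:

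| Decrease rate | ICC 0 | 0.3 | 0.5 | 0.7 |
|---|---|---|---|---|
| 50% | 3.5 | 12.9 | 19.2 | 24.5 |
| 70% | 3.8 | 14.4 | 19.8 | 24.7 |
| 80% | 3.6 | 13.1 | 19.1 | 25.2 |
| 90% | 3.8 | 12.6 | 18.6 | 24.6 |

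Cross-check: with four scores per patient the design effect is 1 + 3 × ICC, and the approximate rejection rate is 2 × [1 − Φ(1.96/√design effect)].
- ICC 0.3: design effect 1.9, rate 15.5%
- ICC 0.5: design effect 2.5, rate 21.5%
- ICC 0.7: design effect 3.1, rate 26.6%

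These sit slightly above the simulation because Fisher's test is conservative.

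**2. Pooled within one period (assumed 8 v 8 patients, 32 v 32 scores).** Percentage rejected:

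| Decrease rate | ICC 0.3 | 0.5 | 0.7 |
|---|---|---|---|
| 50% | 12.4 | 18.0 | 23.0 |
| 70% | 11.5 | 17.4 | 22.9 |
| 80% | 10.4 | 16.1 | 21.3 |
| 90% | 5.8 | 10.5 | 14.5 |

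This is about 6–23% per test; repeat runs move the ends by about one percentage point. With two periods (8 v 8 and 8 v 9), the chance of a false positive in at least one is 1 − (1 − a)(1 − b), where a and b are the two rates. For decrease rates of 70–90% this gives about 17–24% at ICC 0.3 and 34–42% at ICC 0.7.

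**3. One test per day, both periods combined (16 v 17 patients).** Latent-normal correlation between days, 8,000 trials per cell:

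| Decrease rate | One test, % | Any of four, correlation 0 | 0.5 | 0.8 |
|---|---|---|---|---|
| 50% | 3.8 | 13.9 | 12.4 | 10.6 |
| 70% | 2.9 | 11.1 | 10.1 | 9.0 |
| 80% | 2.8 | 11.6 | 11.3 | 9.0 |
| 90% | 1.9 | 6.9 | 5.9 | 5.6 |

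Each test stays below 5%; the chance of at least one false positive among four is about 6–14%.

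**4. One test per day within each period (eight tests).** Same model, 100,000 trials, correlation 0. Any-of-four rates at decrease rates of 50, 70, 80 and 90%:
- 8 v 8: 8.4, 4.7, 1.7 and 0.2%
- 8 v 9: 12.6, 10.9, 5.9 and 1.0%

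Combining the periods as in step 2, for example 1 − (1 − 0.084)(1 − 0.126) = 19.9%, gives 19.9, 15.1, 7.5 and 1.2%. At correlation 0.8 the combined figures are 16.0, 12.3, 6.1 and 1.0%.

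**5. Patient as the unit.** A rank test on each patient's number of decreased scores (0–4), 16 v 17, rejects 4.5–4.8% under the null at ICC 0.3–0.7 (75% decreased, 6,000 trials). One binary outcome per patient with Fisher's test rejects about 1.5–3.5%.

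**The case against.** The strongest objection is that the document never says scores were pooled. The sentence about each form can be read simply as the way increase or decrease was derived, and one Fisher test per form, with one score per patient, fits the wording equally well. This stands. A reader might infer that the trial did count four scores per patient as four patients; the text is silent on that, so 13–25% is a conditional figure and not a description of what was done.

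A second objection also stands. The 16 v 17 figures assume the periods are combined, whereas the section says they were analysed separately. Within periods the size of the problem depends on group sizes and decrease rates that are not given. For per-day tests within periods, Fisher's conservatism in very small samples can keep the overall rate well below 5% when about 90% of scores decrease (step 4).

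A reader might also infer that per-day testing has about half the power of a patient-level summary. That does not hold. It sets one of four tests against a four-day summary and relies on the same effect on every day. Suppose instead that the groups differ only at 24 hours (90% v 40%, then 95% in both; latent correlation 0.5–0.8). The 24-hour Fisher test then has about 83–84% power and the 0–4 count about 67–74%. Comparing groups on a stated day is a legitimate choice.

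None of this supplies the missing definition. The per-day reading removes the dependence problem and leaves multiplicity unaddressed.

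**Conclusion.** The concern holds as an undefined unit of analysis and time point, with no rule for reaching one pain conclusion. It does not hold as a finding that scores were pooled.

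- **If pooled:** about 13–25% false positives at 16 v 17, or about 6–23% per test within an assumed 8 v 8 period, with two such tests. This rests on an ICC of 0.3–0.7 and 50–90% of scores decreased. With no within-patient correlation the 16 v 17 rate would be 3.5–4%.
- **If tested per day:** each test is valid. The chance of at least one false positive is about 6–14% for four tests at 16 v 17. For eight tests across two periods it is about 1–20%.

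Under most of these settings p ≤ 0.05 does not give a 5% error rate for the overall pain claim. The exceptions are mainly very small periods in which nearly all scores decrease. The point should be corrected. Confidence is moderate because the correlation, decrease rates and period sizes are all assumed.

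**What to change.** State that the patient is the unit and that one pain comparison carries the conclusion. For example, count each patient's available postoperative VAS scores that lie below the preoperative VAS (0–4). Compare GWS with EA once by an exact or permutation Wilcoxon test stratified by recruitment period. The text should also give a rule for missing forms and say which of the two preoperative VAS scores is the reference.

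Acceptable alternatives are Fisher's test at one pre-named time point, or four per-day tests with a Holm adjustment. Because the section reports the analysis as already done, the report should say whether the chosen comparison was fixed before the results were seen.

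Whichever comparison is chosen, report the remaining daily counts by group as descriptive, and state that scores from one patient are never pooled into a Fisher table.

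The cost is revised wording and a short re-run on forms already collected. With the summary count, the main result becomes one overall 96-hour statement instead of a claim for each day, and it can be less sensitive if the groups differ on one day only.
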